3.5.1.2 Prior/Concomitant Medications

For prior/concomitant medications, the following imputation rules will be applied to impute start dates under conservative principles:

- If year, month and day are all missing then assign the date of **Day 1 of Volanesorsen**.
- If month and day are missing and year is
 - Earlier than the year of **Day 1 of Volanesorsen** then assign December 31.

- Otherwise, assign January 1.
- If only day is missing and month-year is
 - Earlier than the month-year of **Day 1 of Volanesorsen** then assign the first day of the month.
 - Otherwise, assign the last day of the month.

Imputation will be performed only for the end date only if the day or month is missing (i.e. year is present) for a stopped prior/concomitant medication as follows:

- If month and day are missing then assign December 31.
- If only day is missing then assign the last day of the month.

If the imputed start date is later than the imputed end date then set the imputed start date to the imputed end date.

3.5.2 Adverse Events

3.5.2.1 General Analysis of AEs

All adverse events will be coded by the MedDRA coding system. Missing or partial dates will be imputed as outlined in [section 3.5.1.1](#). A treatment emergent adverse event (TEAE) is defined as any event starting or getting worse on or after **Day 1 of Volanesorsen**

In the situation where change in severity (but no change in seriousness) occurs for an adverse event, study sites are instructed to enter an end date and start a new record for the adverse event. In the new record, the changed severity is to be recorded and the start date will be set to be the end date of the previous record. Data linking those records are collected in the data set “Formlinks”.

TEAE will be identified as follows based on the (imputed) AE start dates:

Case 1: If there is no “Formlink” link, and the AE (start date/time) occurs on or after the patient’s first dosing date/time on **Day 1 of Volanesorsen**, then the AE is treatment-emergent. Otherwise, if the AE (start date/time) occurs prior to the patient’s first dosing date/time on **Day 1 of Volanesorsen**, then the AE is not treatment-emergent.

Case 2: If there is a “Formlink” link between two AE records, then the two AE records will be chronologically ordered by AE start date/time and will be referred to as the “first” and the “second” AE respectively. AE severity (mild/moderate/severe) will then be compared pairwise.

Case 2a: The first AE record in the pair occurs before first dosing on **Day 1 of Volanesorsen**, and the second record occurs on/after dosing.

If the AE severity on the second record is worse than the severity on the first record or the second record is changed to serious, then only count the second AE as treatment-emergent. But, if the severity doesn’t worsen (i.e. the second record severity is the same or less severe than the first

record severity) and the serious result is not changed from non-serious to serious, then neither record is counted as treatment-emergent.

Case 2b: Both AE records in the pair occur on/after first dosing on **Day 1 of Volanesorsen**.

If the AE severity on the second record is worse than the severity on the first record or the second record is changed to serious, then count both records as treatment-emergent. But, if the severity doesn't worsen and the serious result is not changed from non-serious to serious, then only count the first record as treatment-emergent.

Case 2c: Both AE records in the pair occur before first dosing on **Day 1 of Volanesorsen**.

Neither AE is counted as treatment-emergent.

When counting the total number of treatment-emergent events, events linked together through change in severity will still be counted as separate events.

TEAE will be classified into three periods: on-treatment, after-treatment, and post-follow up periods and are defined as follows based on (imputed) start date of the event.

The frequency of patients with any incidence of AEs and the number of events will be summarized by MedDRA preferred term and system organ class for:

1. Any TEAE, any on-treatment TEAE, any after-treatment TEAE.
2. TEAEs related to Study Drug. Related is defined as "Related", "Possible", or missing relationship to Study Drug.
3. Any treatment emergent adverse event by severity. At each level of patient summarization, a patient with multiple events is counted only once according to the worst reported severity. Adverse events with missing severity will be categorized as "Missing" for this summary.
4. TEAEs potentially related to Study Drug by severity.
5. Post-follow up adverse events
6. Serious TEAEs.
7. Serious on-treatment TEAE.
8. Serious TEAEs potentially related to Study Drug.
9. AEs leading to permanent treatment discontinuation, and
10. TEAEs leading to death.

Adverse event summaries will be presented alphabetically and by descending frequency of the percentage of patients in the overall column. An overview of AEs will be provided for all TEAEs, on-treatment TEAEs, and after-treatment AEs. Treatment-emergent AEs, treatment emergent SAEs, AEs that lead to treatment discontinuation, and TEAEs leading to death will be listed. Note that

imputed dates will be used for defining TEAEs and classification of TEAEs into on-treatment, after-treatment, and post-follow up periods. Originally reported dates will be used for listings.

On-study AEs will be also summarized by treatment and age for FCS patients and all patients in safety set.

Treatment emergent renal adverse events will be summarized.

In addition, an overview of adjudicated AEs will be provided for pancreatitis and MACE separately. Adjudicated events will also be listed.

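### SAP 3.5.2.1: Cases 2a and 2b give opposite treatment-emergence verdicts to a post-dose AE record that sits in two linked pairs and is no worse than its predecessor

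*SAP*

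**What the plan says.** Section 3.5.2.1 gives the definition first: "A treatment emergent adverse event (TEAE) is defined as any event starting or getting worse on or after" Day 1 of Volanesorsen. It then explains how linked records arise. When severity changes, "study sites are instructed to enter an end date and start a new record for the adverse event", and for that new record "the start date will be set to be the end date of the previous record". This applies to changes in either direction, so an AE whose severity changes twice has three linked records.

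For linked records, "AE severity (mild/moderate/severe) will then be compared pairwise". There are three cases:

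- **Case 2a** (first record before first dosing, second on or after it). If the second is worse or has become serious, only the second counts. If not, "then neither record is counted as treatment-emergent".
- **Case 2b** (both records on or after first dosing). If the second is worse or has become serious, both count. If not, "then only count the first record as treatment-emergent".
- **Case 2c** (both before first dosing). Neither counts.

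The section adds that records linked through a severity change are each counted as separate events. It gives no order of precedence between the cases and does not limit Case 2b to AEs that began after first dosing.

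**The concern.** The rules are complete for two records but not for three. In a longer chain, a post-dose record can be the second member of a Case 2a pair and the first member of a Case 2b pair. Case 2b always counts the first member of its pair, on the tacit assumption that this record began the event. When that record merely continues an AE present before drug, the assumption fails.

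Two programmers could follow the text faithfully and produce different TEAE flags. The flag feeds most of the AE tables in section 3.5.2.1 and the bleeding summaries in section 3.5.2.3. At stake is whether a patient whose pre-existing AE only improved on drug appears as having had a treatment-emergent event.

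**Working it through.** The SAP states no figure to reproduce; this is a check of logic. Write the severities of three successive linked records as s1, s2, s3, with mild < moderate < severe and seriousness unchanged. A severity change is what opens a new record, so s2 differs from s1 and s3 from s2. That gives 3 × 2 × 2 = 12 sequences. Only adjacent records are compared unless stated otherwise.

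**Record 1 pre-dose, records 2 and 3 post-dose**

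- Pair (1,2), Case 2a: record 2 counts only if s2 > s1.
- Pair (2,3), Case 2b: record 2 always counts; record 3 counts only if s3 > s2.
- Record 2 therefore gets opposite verdicts exactly when s2 < s1.

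The (s1, s2) combinations with s2 < s1 are moderate-mild, severe-mild and severe-moderate. Each allows two values of s3, so 3 × 2 = 6 of 12 sequences conflict. If every pair in the chain is compared, not just neighbours, 7 of 12 conflict.

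The clearest example:

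| Record | Timing | Severity | Case 2a, pair (1,2) | Case 2b, pair (2,3) |
|---|---|---|---|---|
| 1 | pre-dose | severe | not counted | – |
| 2 | post-dose | moderate | not counted | counted |
| 3 | post-dose | mild | – | not counted |

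This AE neither started nor worsened after Day 1 of Volanesorsen, so counting record 2 contradicts the definition.

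**Sequences that never exceed pre-drug severity**

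There are five: moderate-mild-moderate, severe-mild-moderate, severe-mild-severe, severe-moderate-mild and severe-moderate-severe. All five conflict on record 2. In the four rebound sequences (all except severe-moderate-mild), Case 2b also flags record 3, whichever verdict is taken for record 2. In severe-moderate-mild, whether there is any TEAE depends entirely on which case prevails.

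**All three records post-dose**

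Pair (1,2) under Case 2b leaves record 2 out when s2 < s1; pair (2,3) counts it. The same 6 of 12 sequences conflict. Record 1 counts under either reading, so the patient is flagged regardless and only the number of events changes.

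**Where there is no conflict**

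Two-record chains give none. Two pre-dose records followed by one post-dose record give 0 of 12 with adjacent comparison.

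**Size per patient**

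The SAP plans up to approximately 70 patients. One patient whose flag turns on the choice of case moves an overall preferred-term incidence by 1/70 = 1.4 percentage points. The size of the treatment-naive group is not given; for an assumed 20 to 40 patients the step is 1/20 = 5.0 to 1/40 = 2.5 points.

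**The case against.** The strongest reply is that the fault is narrow. It needs an AE still present at first volanesorsen, then two later severity records, the first of them an improvement. Section 3.5 says AE tables present open-label data, and the SAP does not show whether index-study records link into this study's records, so few chains may qualify. There is no formal hypothesis, and by-patient listings would let affected chains be traced. All of this stands and limits the size, but it does not tell a programmer which case to apply.

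A second reply concerns rebounds. In severe-mild-moderate the AE does worsen after Day 1 relative to the record just before, and the SAP names no reference severity. Flagging it is therefore defensible. This also stands: only the purely improving chain plainly contradicts the definition.

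A reader might further infer that a pre-drug AE becoming serious on drug is lost, because the linking instruction covers only this situation: "In the situation where change in severity (but no change in seriousness) occurs for an adverse event". The document does not support that. What sites do when seriousness changes is left to instructions not shown, and Cases 2a and 2b provide for a second record that has become serious, which suggests such links are expected.

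**Conclusion.** The contradiction holds on the text alone. Cases 2a and 2b disagree about any post-dose record that follows a more severe record in its chain and is itself followed by another linked record. In the improving pre/post/post chain, one of the two answers breaches the SAP's definition. The rebound chains are an ambiguity about the reference severity, and the wholly post-dose chains affect event counts only.

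Three stronger readings are not supported:

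- **All longer chains are affected.** They are not; half of the pre/post/post sequences get a consistent answer with adjacent comparison.
- **Each affected chain adds a fixed number of false TEAEs.** For the improving chain the text gives two answers, and one of them is zero.
- **Injection-site tables are materially distorted.** The main definition of local cutaneous reactions requires onset on the day of injection, and no study injection before Day 1 is described for newly enrolled patients.

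The number of affected chains is unknown, so the total effect cannot be stated. The counts above assume that every severity change opens a record, that seriousness is unchanged, and that links run between neighbouring records. This is a modest but real defect in a derivation behind the main safety tables, and worth correcting because the remedy is cheap.

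**What to change.** Replace the pairwise comparison with a whole-chain rule:

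- **(a) Chain starting before first dosing.** A post-dose record is treatment-emergent only if it is newly serious, or is both more severe than the last pre-dose record (the reference Case 2a already uses) and more severe than the record immediately before it.
- **(b) Chain starting on or after first dosing.** The first record is treatment-emergent. A later record is treatment-emergent only if it is more severe than its immediate predecessor or newly serious.

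Checked against the 12 pre/post/post sequences, (a) gives no TEAE in the five that never exceed pre-drug severity and one (record 3) in moderate-mild-severe. It leaves the six non-conflicting sequences as they are now. Mild-severe-moderate, for example, keeps its single TEAE and does not gain one for the improving step. Rule (b) counts only record 1 in a wholly post-dose severe-moderate-mild chain.

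Rule (a) settles the rebound question by naming a reference. If the sponsor wants rebounds counted, or prefers the worst pre-dose severity as reference, the SAP should say so. The choice matters for an AE that had already improved before first dosing and then returns to its earlier level.

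The cost is a few lines of SAP text, a small change to the TEAE derivation and a rerun of the tables that use the flag. No new data are needed. A count of chains with three or more linked records would show how many patients are affected.

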1.1 Study Overview

This is an open-label study of:

Group 1: ISIS 304801-CS6 (index study) roll over FCS patients

Group 2: ISIS 304801-CS16 (index study) roll over FCS patients

Group 3: FCS patients who did not participate in the ISIS 304801-CS6 or ISIS 304801-CS16 index studies.

Up to approximately 70 patients will receive 300 mg once weekly volanesorsen for 52 weeks in the CS7 study.

Following the Week 52 visit, patients will have the option of participating in an expanded access program or continuing dosing for up to an additional 52 weeks until an expanded access program is approved and available in their country. Patients not participating in an expanded access program will enter a 13-week post-treatment evaluation period.

There is no primary efficacy endpoint. Both efficacy endpoints and safety endpoints will be summarized to evaluate the safety and efficacy of extended dosing with volanesorsen sodium 300 mg in patients with FCS.

Groups 1 and 2 (Qualification): During the qualification period, the eligibility of the patient to enroll in the open-label study will be determined. Final assessments from the ISIS 304801-CS6 or ISIS 304801-CS16 studies may be used for qualification. A period of up to 2 weeks after completion of the ISIS 304801-CS6 or ISIS 304801-CS16 index studies (unless approved by the Sponsor) is given to complete qualification. Qualified patients will retain the unique patient identification number that was assigned to them during the ISIS 304801-CS6 or ISIS 304801-CS16 index studies.

Group 3 (Screening and Qualification): At the time of consent, the patient will be considered enrolled into the study and will be assigned a unique screening number before any study procedures, including screening procedures, are performed.

Patients will be enrolled into the treatment phase of the study after all Screening (Group 3) and qualification assessments have been completed and after the Investigator has verified that they are eligible per criteria in protocol Sections 5.1 and 5.2. No patient may begin treatment prior to enrollment.

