2.1.3 Extended Treatment Period

Patients will have the option of continuing treatment for up to an additional 52 weeks until an expanded access program is approved and available in their country.

During the extended treatment period, patients will report to the study center for clinic visits during Weeks 54-104 (see Schedule of Procedures in Appendix A of the protocol). Study Drug will be administered once weekly unless the patient is on a biweekly treatment schedule for safety reasons. Collection and measurement of vital signs, clinical laboratory parameters (including hematology, serum chemistry, and urinalysis), AEs, concomitant medication/procedure information, lipid panel, volanesorsen plasma concentrations, IM testing, ECGs, and physical examinations will be performed according to the Schedule of Procedures in Appendix A. Adverse events at the injection site should

be collected as adverse events. Dietary counseling will be reinforced at intervals throughout the extended treatment period. All blood and urine samples should be collected prior to volanesorsen administration. Blood sampling at Weeks 53, 54, 55, 56, 57, 58, 59, 60, 61, 62, 63, 65, 66, 67, 68, 69, 70, 71, 72, 73, 74, 75, 77, 78, 79, 80, 81, 82, 83, 84, 85, 86, 87, 88, 89, 91, 92, 93, 94, 95, 96, 97, 98, 99, 100, 101, 102, and 103 may be conducted by a home healthcare nurse. Approval for study procedures to be conducted by a home healthcare nurse on other outpatient visit days will require prior approval by the Sponsor. Patients must be fasted prior to drawing all blood samples and samples drawn locally should also be sent to the central laboratory for analysis whenever possible. Treatment instructions and training will be provided to the patient where applicable.

2.1.4 *Pharmacokinetic (PK) Subgroup*

A subgroup of patients will participate in an extended PK collection. Patients in this subgroup will have more frequent PK sampling over a 24-hour period following the first dose on Study Day 1 in order to evaluate the plasma PK parameters of volanesorsen. Patients in this subgroup will have an additional visit to the clinic, or by a home healthcare nurse, on Day 2 to collect a 24-hour post-dose blood draw after dosing on Day 1. The detailed PK sampling schedules are outlined in Appendix C of the protocol.

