	104	722	674 to 743
	117	813	744 to 858
	130 (France)	904	859 to 949
Abdominal Pain			
	m	$n \times 7 + 1$	$mx7+3 \text{ to } mx7-3,$ $m = -1, -2, \dots$
	...		
	-2	-13	-11 to -17
	-1	-6	-4 to -10
	1	1	1 to -3
	2	8	5 to 11

	3	15	12 to 18
	n	(n-1) × 7+1	(n-1) × 7-2 to (n-1) × 7+4
	...		
MRI			
	Screening	NA	≤ 14
	52	358	298 to 418
Quality of Life Assessments (EQ-5D, SF-36)			
	1	1	1
	13	85	55 to 115
	26	176	146 to 206
	52	358	328 to 404
	65	449	405 to 479
	78 (France)	540	496 to 570
	117 (France)	813	769 to 843
	130 (France)	904	860 to 934

Note: Regarding lipid measurements for efficacy analyses, mapped observed assessments defined in this table will be derived further. The derivations for baselines are described in [section 3.2.3](#). The derivations for Month 3, 6 and 12 are described in [section 3.3.1](#).

Non-efficacy by visit assessments will be summarized using the visit labels provided in the data. Multiple results with the same visit label will be averaged.

Unscheduled results and data from local labs will not be included in the by visit summaries but will be used in the determination of baseline, in the laboratory abnormality, stopping rule, and platelets reduction analyses presented in data listings.

Unscheduled results from the central lab will be used in the determination of baseline, laboratory abnormality summaries, and shift from **safety baseline** to worst post-baseline, and platelets reduction analyses only, and presented in data listings. Local lab data will be only used in platelet analyses (including by visit summaries, abnormality summary, shift from Baseline to worst post-baseline, reduction analyses), and presented in data listings.

Summary tables and figures will NOT be presented by the treatment group in each index study (ISIS 304801-CS6 or ISIS 304801-CS16) and the newly enrolled patients as a separate group per protocol. Per Sponsor decision, most summary tables and figures will be presented in the following groups, i.e. Treatment naive group, CS6-Volanesorsen, CS16-Volanesorsen, and Overall, if applicable.

Note: “Treatment naive group” for most tables and figures is a combined group of subjects including CS7-New, CS6-Placebo and CS16-Placebo. When the summary is based on **Index Study Baseline**, “Treatment naive group” is a combined group of subjects including CS6-Placebo and CS16-Placebo.

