3.3.9 Adjudicated acute pancreatitis events Rate

Yearly rate of adjudicated acute pancreatitis events and patient reported moderate or severe abdominal pain (pain score: 4-10) for FAS during the on-treatment period of the Open-label study, calculated as $365.25 \times \text{the number of events during the on-treatment period} / \text{on-treatment duration}$, will be summarized with descriptive statistics. At each mapped visit window of abdominal pain, at most one moderate or severe event will be counted to calculate the yearly rate. Adjudicated acute pancreatitis event rate prior to first dose of Study Drug (including events based on medical chart review) vs. treatment emergent events will be summarized.

Yearly rate of adjudicated acute pancreatitis events and patient reported moderate or severe abdominal pain (pain score: 4-10) for patients who administered volanesorsen in Index studies will be calculated and summarized, including events occurred during either index study or open-label study.

On-study and on-treatment pancreatitis incidence rate per patient year of exposure will be summarized.

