3.5 Safety Analyses

Safety endpoints including treatment exposure, AEs, clinical safety lab, vital signs, physical examination, 12-lead ECG, Echocardiogram, prior and concomitant medication use, and MRIs will be summarized in Safety Set.

On-Study period (from **Day 1 of Volanesorsen** to end of the study) in the open-label study will be classified to 3 periods:

- On-treatment period: from the first dose of Volanesorsen to the last dose of Volanesorsen + 28 days
- After-treatment period: from the last dose of Study Drug + 29 days to the last dose of study medication + 90 days
- Post-follow up period: after the last dose of Study Drug + 90 days

For vital sign, clinical safety lab, or 12-lead ECG,

- Visits of summary tables include baseline and labeled post baseline visits in the open-label study.
- **Safety Baseline** is defined in the [section 3.2.3](#) of this SAP.

For AEs, prior and concomitant medication use, each summary table will present the open-label study data.

For treatment exposure, details are discussed in the [section 3.5.5](#) of this SAP.

By patient data listings will display data collected in the open-label study.

In this section, **Day 1 of Volanesorsen** is defined as the first day volanesorsen is administered to the patient. For patients on active treatment in the index study, Day 1 of Volanesorsen will be the first day volanesorsen is administered in the index study. For patients on placebo in the index study, Day 1 of Volanesorsen will be the first day volanesorsen is administered in this open-label study.

Patient profile figures will be generated for selected patients to provide graphical profile of endpoint of interest.

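### The general, serious, discontinuation and bleeding AE tables give only crude percentages and event counts, although individual open-label observation can run from weeks to over two years

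*SAP*

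**What the plan says.** Section 3.5.2.1 lists ten AE summaries, including any TEAE, serious TEAEs and AEs leading to permanent discontinuation, under one measure: "The frequency of patients with any incidence of AEs and the number of events will be summarized by MedDRA preferred term". Ordering also rests on the crude figure: "Adverse event summaries will be presented alphabetically and by descending frequency of the percentage of patients in the overall column". Section 3.5.2.3 applies the same measure to bleeding events. The columns come from section 3.2.1: "most summary tables and figures will be presented in the following groups, i.e. Treatment naive group, CS6-Volanesorsen, CS16-Volanesorsen, and Overall".

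The data window is set in section 3.5: "For AEs, prior and concomitant medication use, each summary table will present the open-label study data".

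Length of observation varies by patient. Section 1.1 plans the core period: "Up to approximately 70 patients will receive 300 mg once weekly volanesorsen for 52 weeks in the CS7 study". Section 2.1.3 then gives patients the "option of continuing treatment for up to an additional 52 weeks until an expanded access program is approved". Under section 2.1.5, only patients who do not enter expanded access have the 13-week follow-up, which ends at Week 65 or, after the extension, at Week 117. The on-treatment period in section 3.5 closes 28 days after each patient's last dose, so it varies too.

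The SAP does use time or dose denominators elsewhere. Section 3.2.1 defines total patient-years, section 3.2.4 applies them to discontinuation, and section 3.3.9 to pancreatitis: "On-study and on-treatment pancreatitis incidence rate per patient year of exposure will be summarized". Section 3.5.2.3 also gives local injection-site reactions and flu-like reactions as a percentage of injections.

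**The concern.** A crude percentage rises with time observed. If one column holds more patients who stop early, or fewer who extend, its AE percentages are lower even when the risk per unit time is the same. Event counts behave likewise. The Overall column mixes patients seen for a few weeks with patients seen beyond Week 104, so its percentage is not a risk over any stated period.

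Part of the variation in follow-up is administrative (when expanded access opens in a country), but part may be caused by toxicity. A patient withdrawn for toxicity leaves the on-treatment risk window yet stays in the full denominator. Section 1.2 makes safety of extended dosing an objective alongside efficacy, and these are the tables most readers will use for it.

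**Working it through.** The SAP states no AE rate, sample size or retention figure, so there is nothing of its own to reproduce. What follows is illustration under stated assumptions.

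**Inputs from the SAP.** Core treatment is 52 weeks and the extension 0 to 52 weeks. Follow-up is 13 weeks or none. The last scheduled visit outside France is Week 117, Day 813: 813/365.25 = 2.23 years. The France window at Week 130 is centred on Day 904: 904/365.25 = 2.48 years.

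**Assumptions.** The first-event hazard r is constant and equal in all patients: 0.10, 0.25, 0.50 or 1.0 per patient-year. A year has 52.18 weeks.

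**Step 1, one patient.** P(at least one event by time t) = 1 - exp(-r t).

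| r per patient-year | 6 wk | 26 wk | 52 wk | 65 wk | 117 wk |
|---|---|---|---|---|---|
| 0.25 | 2.8% | 11.7% | 22.1% | 26.8% | 42.9% |
| 0.50 | 5.6% | 22.1% | 39.2% | 46.4% | 67.4% |
| 1.0 | 10.9% | 39.2% | 63.1% | 71.2% | 89.4% |

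**Step 2, two groups with equal risk.** The group percentage is the Step 1 figure averaged over observation times.

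- Mild contrast, early stopping only: 40% vs 20% are observed for 26 weeks and the rest for 65 weeks.
- Wide contrast: group A has 50% observed 26 weeks and 50% observed 65 weeks; group B has 20% observed 26 weeks and 80% observed 117 weeks. Patient-years per patient are (0.5 x 26 + 0.5 x 65)/52.18 = 0.87 and (0.2 x 26 + 0.8 x 117)/52.18 = 1.89.

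| r | Mild contrast | Gap (points) | Wide contrast | Gap (points) |
|---|---|---|---|---|
| 0.10 | 9.0% vs 10.3% | 1.3 | 8.3% vs 17.0% | 8.7 |
| 0.25 | 20.7% vs 23.8% | 3.1 | 19.2% vs 36.7% | 17.5 |
| 0.50 | 36.6% vs 41.5% | 4.9 | 34.2% vs 58.3% | 24.1 |
| 1.0 | 58.4% vs 64.8% | 6.4 | 55.2% vs 79.4% | 24.2 |

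With r = 0.50 in the wide contrast, expected events per 20 patients are 20 x 0.50 x 0.87 = 8.7 and 20 x 0.50 x 1.89 = 18.9.

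**Step 3, a second wide contrast.** Let the risk be 30% by Week 52, so h = -ln(0.70) = 0.357 per 52 weeks. Then 1 - exp(-h/2) = 16.3% at Week 26 and 1 - exp(-2h) = 51.0% at Week 104. If half of a group stops at Week 26 and the rest at Week 52, the figure is 0.5 x 16.3 + 0.5 x 30 = 23.2%. If half stops at Week 52 and half at Week 104, it is 0.5 x 30 + 0.5 x 51.0 = 40.5%. The gap is about 17 points.

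**Step 4, the proposed measures.** Under a constant hazard, expected first events per patient are 1 - exp(-r t), and expected time at risk up to the first event or t is (1 - exp(-r t))/r. Their ratio is r for any t, so the first-event rate is equal in both groups of every contrast above. Restricting Step 3 to Weeks 0-52 gives 23.2% vs 30%: the gap falls from about 17 to about 7 points. The restricted window therefore removes the effect of extension but not that of early stopping, and both measures are needed.

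**The case against.** Five points on the other side have weight.

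- **Some AE results already have a denominator.** Injection-site and flu-like reactions are given per injection. Adjudicated pancreatitis, itself an AE endpoint in section 1.4.2, has a patient-year rate. A reader might infer that all AE results are crude; the SAP does not support that. This stands, and it confines the point to the tables named in the heading.
- **Early stopping is not hidden.** The SAP plans discontinuations by month with reasons, a rate per patient-year and Kaplan-Meier plots of treatment continuation (section 3.2.4), a listing of stopping-rule terminations (section 3.5.4.2) and treatment duration by category (section 3.5.5). This stands too, but a reader cannot recover first-event rates from these separate displays.
- **All groups share one planned open-label schedule.** The range from weeks to over two years describes patients, not columns. A reader might take 17 points as the expected distortion; it is a chosen contrast, and nothing in the SAP says that retention or extension will differ so much.
- **Stopping treatment does not end observation for all-TEAE tables.** Section 2.1.2 monitors early stoppers for at least 12 weeks and encourages landmark visits to Week 52. With full attendance and an unchanged hazard, the first group in Step 3 would show 30%, not 23.2%. The low figures fit the on-treatment tables best.
- **A person-year rate is not neutral.** If events cluster early, long extension time dilutes it and the longest-treated group looks safer. Neither measure removes the selection of rollover patients who have already tolerated the drug.

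**Conclusion.** The point holds for the general TEAE, serious TEAE, discontinuation-AE and bleeding tables. Without person-time or a common window, equal risks can give different percentages across columns, and the Overall percentage refers to no defined period.

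The size cannot be fixed from the SAP. At assumed constant hazards of 0.10 to 1.0 per patient-year, the gap is about 1 to 6 points if groups differ only in early stopping (40% vs 20%). It is about 9 to 24 points if they also differ strongly in extension, with about 17 at hazards of 0.25 to 0.36. It is smaller for all-TEAE tables when early stoppers attend later visits.

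A reader might also infer that the safety conclusions are invalid or that an error rate is inflated. Neither follows: sections 1.3 and 3.1 set no formal hypothesis and evaluate safety by summary tables. What suffers is interpretation, and the remedy is cheap.

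**What to change.** Keep the percentages and counts. For any TEAE, serious TEAEs, AEs leading to discontinuation, bleeding and platelet events, add in the same columns the number of patients with a first event per 100 patient-years at risk, and show the patient-years.

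Define time at risk explicitly. The section 3.2.1 patient-year total runs to the latest visit or data cutoff and does not stop at a first event, so it cannot serve unchanged.

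- **Start:** the first open-label dose, for all groups. Day 1 of Volanesorsen lies in the index study for patients treated actively there, while the AE tables hold open-label data; using it would mismatch numerator and denominator.
- **End, on-treatment tables:** the first event, or the last open-label dose + 28 days.
- **End, all-TEAE tables:** the first event, or last contact.

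Also show incidence restricted to open-label Weeks 0-52.

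The cost is a few extra columns and one restricted table, from dates already held. The rates assume a roughly constant hazard. The Weeks 0-52 table helps check this, since early clustering would show as a higher rate there than over the whole period. A footnote should say that selection of rollover patients remains.
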